6.7 Management of study drug related toxicities

If a patient experiences a CTCAE grade 3 and/or unacceptable toxicity not attributable to the disease or disease-related processes under investigation, dosing will be interrupted and supportive therapy administered as required in accordance with local practice/guidelines.

If a toxicity resolves or reverts to ≤CTCAE grade 2 within 3 weeks of onset, treatment with study drug may be restarted at the same dose (80 mg) or a lower dose (40 mg) using the rules below for dose modifications (Table 3) and with discussion and agreement with the AstraZeneca Study Team Physician as needed. There will be no individual modifications to dosing schedule in response to toxicity, only potential dose reduction or dose interruption.

If the toxicity does not resolve to ≤CTCAE grade 2 after 3 weeks, then the patient should be withdrawn from the study and observed until resolution of the toxicity.

Table 3. OSIMERTINIB dose adjustment information for adverse reactions

Target		
organ	Adverse reaction ^a	Dose modification
Pulmonary	ILD/Pneumonitis	Permanently discontinue OSIMERTINIB
Cardiac	QTc interval greater than 500 msec on at least 2 separate ECGs	Withhold OSIMERTINIB until QTc interval is less than 481 msec or recovery to baseline if baseline QTc is greater than or equal to 481 msec, then restart at a reduced dose (40 mg)
	QTc interval prolongation with signs/symptoms of serious arrhythmia	Permanently discontinue OSIMERTINIB
Other	Grade 3 or higher adverse reaction	Withhold OSIMERTINIB for up to 3 weeks
	If Grade 3 or higher adverse reaction improves to Grade 0-2 after withholding of OSIMERTINIB for up to 3 weeks	OSIMERTINIB may be restarted at the same dose (80 mg) or a lower dose (40 mg)
	Grade 3 or higher adverse reaction that does not improve to Grade 0-2 after withholding for up to 3 weeks	Permanently discontinue OSIMERTINIB

^a Note: The intensity of clinical adverse events graded by the National Cancer Institute (NCI) Common Terminology Criteria for Adverse Events (CTCAE) version 4.0.

ECGs: Electrocardiograms; QTc: QT interval corrected for heart rate

On resolution of toxicity within 3 weeks:

• If an AE subsequently requires dose interruption, study drug may restart at the same dose or the reduced dose, on resolution/improvement of the AE at the discretion of the Investigator.

ILD/Pneumonitis-like toxicity

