If new or worsening pulmonary symptoms (e.g., dyspnoea) or radiological abnormality suggestive of interstitial lung disease is observed, an interruption in study treatment dosing is recommended, and the AstraZeneca study team should be informed. It is strongly recommended to perform a full diagnostic workup, to exclude alternative causes such as lymphangitic carcinomatosis, infection, allergy, cardiogenic edema, or pulmonary hemorrhage. The results of the full diagnostic workup (including high-resolution computed tomography, blood and sputum culture, haematological parameters) will be recorded in the CRF by the investigator. In the presence of confirmatory HRCT scans where other causes of respiratory symptoms have been excluded, a diagnosis of interstitial lung disease (ILD) should be considered and study treatment permanently discontinued.

In the absence of a diagnosis of ILD study treatment may be restarted following consultation with the AstraZeneca Study Team Physician.

QTc prolongation

Patients with QTcF prolongation to >500 msec should have study treatment interrupted and regular ECGs performed until resolution to <481 msec or recovery to baseline if baseline QTcF is >481 msec and then restarted at a reduced dose of 40 mg. If the toxicity does not resolve to ≤grade 1 within 21 days the patient will be permanently withdrawn from study treatment.

Keratitis

Patients presenting with signs and symptoms suggestive of keratitis such as acute or worsening: eye inflammation, lacrimation, light sensitivity, blurred vision, eye pain and/or red eye should be referred promptly to an ophthalmology specialist.

Changes in cardiac contractility

In patients with cardiac risk factors and those with conditions that can affect LVEF, cardiac monitoring, including an assessment of LVEF at baseline and during treatment, should be considered. In patients who develop relevant cardiac signs/symptoms during treatment, cardiac monitoring including LVEF assessment should be considered.

Patients experiencing corneal ulceration, Interstitial Lung Disease (ILD) or QTc prolongation with signs/symptoms of serious arrythmia will not be permitted to restart study treatment.

For the details, please refer to the local prescribing information.

7. Study Drug and Other Treatments

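### Protocol Section 6.7 gives two conflicting QTc interruption rules and differing recovery conditions, so sites can interrupt or discontinue osimertinib on different grounds

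*Protocol*

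**What the plan says.** Protocol Section 6.7 states the QTc action twice.

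- **QTc paragraph.** "Patients with QTcF prolongation to >500 msec should have study treatment interrupted", with regular ECGs "until resolution to <481 msec or recovery to baseline if baseline QTcF is >481 msec and then restarted at a reduced dose of 40 mg". It then adds: "If the toxicity does not resolve to ≤grade 1 within 21 days the patient will be permanently withdrawn from study treatment".
- **Table 3, cardiac row.** Drug is withheld for "QTc interval greater than 500 msec on at least 2 separate ECGs", until the interval is "less than 481 msec or recovery to baseline if baseline QTc is greater than or equal to 481 msec", and then restarted at 40 mg. The row gives no time limit and no grade.

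Three other places bear on the same patient:

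- The general rule that opens Section 6.7 asks for resolution to CTCAE grade 2 or less after 3 weeks, failing which the patient leaves the study.
- Section 3.9 makes discontinuation permanent when a drug-related AE needs a hold of more than 21 days. It also says that stopping treatment is not automatic withdrawal from the study.
- Sections 6.7 and 7 refer to the local prescribing information, which is not among the documents.

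On reporting, Protocol Section 6.3.6 makes deterioration in a mandated assessment an AE only if it meets an SAE criterion or is the reason for discontinuing study drug. SAP Section 8.7.1 summarises AEs of special interest (QTc prolongation is an example) and TEAEs leading to dose change, interruption or discontinuation. SAP Section 8.7.4 tabulates categories of the maximum post-dose QTc.

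**The concern.** A dosing rule for a named cardiac risk should give one answer for one ECG. Here an investigator who reads the paragraph and one who reads the table can reach different decisions on the same tracing. They can also reach different decisions three weeks later on whether the patient may restart, must stop treatment, or must leave the study. The synopsis lists QTc prolongation among the risks to be closely monitored, so this is first a patient-safety matter. It is secondarily a data matter. Whether a patient is discontinued can decide whether a QTc finding becomes an AE at all, and with 60 patients each one is 1/60 = 1.7 percentage points.

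**Working it through.** **Step 1: set the rules side by side.**

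| Element | QTc paragraph, 6.7 | Table 3 QTc row, 6.7 | General rule, 6.7 | Section 3.9 |
|---|---|---|---|---|
| Trigger | QTcF >500 msec, number of ECGs not stated | QTc >500 msec on at least 2 ECGs | grade 3 and/or unacceptable toxicity | – |
| Correction | QTcF | not named | – | – |
| Release | <481 msec | <481 msec | grade 2 or less | – |
| Baseline exception | >481 msec | ≥481 msec | – | – |
| Time limit | 21 days, to grade 1 or less | none | 3 weeks, to grade 2 or less | hold of more than 21 days for a drug-related AE |
| Consequence | off treatment | none stated | off study | off treatment |
| Restart dose | 40 mg | 40 mg | 80 or 40 mg | – |

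The two QTc rules agree on the 500 msec threshold, the 481 msec release and the restart dose. They disagree on:

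1. **Trigger.** With exactly one reading above 500 msec, the paragraph is met and the Table 3 QTc row is not. This is a direct conflict.
2. **Recovery grade and consequence.** Grade 1 with loss of treatment, grade 2 with loss of study participation, or neither, depending on where one reads.
3. **Correction formula.** Named in one place and left open in the other. This is under-specification, not two rival formulas.
4. **Baseline boundary.** "recovery to baseline if baseline QTcF is >481 msec" against "recovery to baseline if baseline QTc is greater than or equal to 481 msec". These differ only at exactly 481 msec, which is minor.

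**Step 2: trace the effect on reported results.** An interruption alone is not an AE under Section 6.3.6. A discontinuation is one route by which a QTc finding becomes an AE. So the trigger conflict does not by itself feed the AE tables, but the differing stop conditions can. Section 7 requires interruptions and reductions to be recorded. The SAP exposure formula (last dose date − first dose date + 1) is not shortened by an interruption but is shortened by an early stop. The SAP 8.7.4 categories take the maximum QTc whichever dosing rule a site follows, apart from any effect of interruption on later readings.

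**Step 3: illustrate the trigger conflict.** The plan gives no QTc figure to reproduce. Its only computed figures, the exact confidence limits for n = 60, do reproduce and are not affected.

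Assumptions, not from the documents: on-treatment mean QTcF 430 to 440 msec, between-patient SD 20 to 25, within-patient SD 8 to 15, independent readings. The schedule gives six post-dose ECGs (Day 1 of Cycles 2 to 6, and EOT). For a patient with true mean m, let p = P(reading > 500 | m). Then:

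- at least one of six: 1 − (1 − p)^6
- at least two of six: 1 − (1 − p)^6 − 6p(1 − p)^5

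Averaged over patients and multiplied by 60:

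| Mean, between SD, within SD | At least 1 | At least 2 of 6 | Difference | Ratio |
|---|---|---|---|---|
| 430, 20, 8 (smallest difference) | 0.12 | 0.05 | 0.07 | 2.5 |
| 430, 20, 15 (largest ratio) | 0.69 | 0.16 | 0.53 | 4.4 |
| 440, 25, 8 (smallest ratio) | 1.53 | 0.92 | 0.61 | 1.7 |
| 440, 25, 15 (largest difference) | 3.81 | 1.65 | 2.16 | 2.3 |

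Across the assumed ranges the single-reading rule triggers 0.1 to 2.2 more patients of 60.

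**The case against.** The best defence is that a common reference exists. Section 6.7 closes by pointing to the local prescribing information, Section 7 says dose modification follows it, and investigators are trained on it before first enrolment. That makes divergence less likely, so the supportable word is that sites can act differently, not that they will. It does not cure the text. The two literal triggers differ, so at least one departs from whatever the label says, and each passage carries conditions that the other lacks, so neither is merely a summary.

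Other parts of the defence stand. The paragraph does not say one ECG; it gives no number, and one reading satisfies it. Section 3.9 supplies a 21-day limit for drug-related AEs, so the Table 3 row is not wholly without a deadline. The synopsis allows safety assessments more often if clinically indicated, so a second ECG need not wait 21 days for the next cycle.

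A reader might go further in three ways that the documents do not support:

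- **That QTc events will be counted differently across sites.** The maximum-QTc table is independent of the dosing rule and interruption alone is not an AE. There is thus no reason for the SAP categories to cite the dosing rule. That no document defines a QTc event of special interest is a separate gap.
- **That a patient with baseline above 481 msec can never satisfy the grade 1 condition.** This depends on where grade 1 ends, which the documents do not give, and such a patient could later read below baseline.
- **That the triggers differ by a large fixed multiple.** Comparing one given ECG with two given ECGs in a single patient near 500 msec inflates the contrast, because Table 3 does not specify which two. With a true QTcF of 490 msec and within-patient SD 10 or 15, six ECGs give 65% against 24%, or 83% against 47%: 2.6- and 1.8-fold, for a hand-picked patient.

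**Conclusion.** The contradiction is real and rests on the text alone. After one reading above 500 msec, Section 6.7 directs two different actions. Its recovery grade, deadline and consequence also differ between the paragraph, the table and the general rule, with Section 3.9 adding its own hold limit. Sites can therefore interrupt or discontinue on different grounds. Confidence is high for the trigger and recovery-grade mismatch.

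The size is modest and rests wholly on assumed QTc distributions: from near zero to about 2 patients of 60 for the trigger. The effect on results is indirect, through exposure data and through QTc findings that become AEs only because drug was stopped. No sample size or confidence interval figure is affected. The change should be made because of the safety rule, not because it alters the analysis.

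**What to change.** Reconcile the QTc paragraph and the Table 3 QTc row of Section 6.7 with each other, with the general rule of that section, with Section 3.9 and with the cited local prescribing information. State one rule that fixes:

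- the number of ECGs needed
- the correction formula
- the baseline boundary
- the recovery grade and time limit
- whether failure to recover means off treatment or off study
- how the baseline exception relates to the grade condition

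Which rule stands is for the sponsor's clinical team; this review takes no view. The SAP QTc categories need no change on this account. The cost is protocol wording and a memo to sites; reconciling the wording does not in itself call for a new procedure.

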3.9 Discontinuation from study treatment

If a subject's study treatment must be discontinued, this will not result in automatic withdrawal of the subject from the study. If a subject discontinues study treatment for any reason before the end of the treatment phase, end-of-treatment assessments should be obtained and scheduled follow-up phase assessments should continued as specified in the Time and Events Schedule.

Patients may be discontinued from the study drug treatment in the following situations:

- The subject experiences disease progression (as per participating physician's assessment)
- Adverse Event (including laboratory abnormality or intercurrent illness) which, in the opinion of the investigator, indicates that continued participation in the study is not in the best interest of the patient
- The subject (or the subject's legally acceptable representative) withdraws consent for administration of study drug
- The subject received concurrent (non-protocol) anti-cancer treatment for NSCLC
- ILD/Pneumonitis
- Corneal ulcerations
- QTc interval prolongation with signs/symptoms of serious arrhythmia
- Pregnancy
- Any adverse event deemed to be related to osimertinib that requires a dose hold of more than 21 days will result in permanent discontinuation of osimertinib.
- Grade 3 or higher adverse reaction that does not improve to Grade 0-2 after withholding for up to 3 weeks

The primary reason for discontinuation of study treatment is to be recorded in the eCRF.

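### Section 6.7 bars restart after corneal ulceration, but Table 3 in the same section has no entry for it and leaves it under rows that can permit restart

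*Protocol*

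**What the plan says.** Four places in Protocol Section 6.7 and one in Section 3.9 bear on restarting study drug after corneal ulceration.

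- **Section 6.7, text before Table 3.** When a toxicity has come down to Grade 2 or lower within 3 weeks, drug may be restarted at 80 mg or 40 mg, "using the rules below for dose modifications (Table 3"). The study team physician is to be consulted as needed.
- **Section 6.7, Table 3.** ILD/pneumonitis and QTc prolongation with serious arrhythmia each have a row reading "Permanently discontinue OSIMERTINIB". Corneal ulceration and keratitis have no row. Under *Other*, the condition is "If Grade 3 or higher adverse reaction improves to Grade 0-2 after withholding of OSIMERTINIB for up to 3 weeks" and the action is "OSIMERTINIB may be restarted at the same dose (80 mg) or a lower dose (40 mg").
- **Section 6.7, bullet after Table 3.** After a later interruption, restart at the same or the reduced dose is left to the investigator.
- **Section 6.7, closing text.** "Patients experiencing corneal ulceration, Interstitial Lung Disease (ILD) or QTc prolongation with signs/symptoms of serious arrythmia will not be permitted to restart study treatment".
- **Section 3.9.** "Corneal ulcerations" is one item in a list introduced by "Patients may be discontinued from the study drug treatment in the following situations".

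The Keratitis paragraph of Section 6.7 asks for prompt referral to an ophthalmologist and gives no dosing action. Sections 6.7 and 7 both defer to the local prescribing information.

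**The concern.** The closing text names three events after which restart is barred. Table 3 carries that bar for two of them. The third has no row of its own, so a site using the table has only the *Other* rows to apply, and these can lead to a restart. No passage says whether the table or the text prevails.

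The layout makes the bar easy to miss. It is not in the Keratitis paragraph. It comes after the paragraph on cardiac contractility, so someone who checks Table 3 and then the Keratitis paragraph would not meet it.

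Safety is the trial's only objective, and about 10 sites will apply these rules independently. One site could re-expose a patient whom the same section bars from restarting, while another stops the drug for the same event.

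**Working it through.** No figure in the plan depends on this point, so the check is a comparison of passages.

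**Step 1. Coverage of the three named events in Table 3.**

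| Event named in the closing text of 6.7 | Permanent-discontinuation row in Table 3 |
|---|---|
| ILD | Yes |
| QTc prolongation with serious arrhythmia | Yes |
| Corneal ulceration | No |

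Two of the three are covered.

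**Step 2. What each passage directs, by course of the event.**

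| Course of the corneal ulceration | Table 3, *Other* rows | Closing text of 6.7 | Section 3.9 | Result |
|---|---|---|---|---|
| (a) Grade 3 or higher, improving to Grade 0-2 within the hold | Restart allowed, 80 mg or 40 mg | Restart barred | May be discontinued | Conflict |
| (b) Grade 3 or higher, not improving within the hold | Permanent discontinuation | Restart barred | May be discontinued | Table and text agree |
| (c) Below Grade 3 | Silent | Restart barred | May be discontinued | No conflict with the table, which gives no instruction |

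**Step 3. Reach of the other restart provisions.** The text before the table covers unacceptable toxicity as well as Grade 3, and the bullet after the table sets no grade limit. Neither excepts corneal ulceration. The tension within Section 6.7 can therefore extend somewhat beyond course (a), although the conflict with Table 3 itself does not.

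**Step 4. Strength of Section 3.9.** Its list is permissive. Where that section intends a permanent stop it says so, as for a drug-related event that "requires a dose hold of more than 21 days will result in permanent discontinuation of osimertinib". The corneal ulceration item has no such wording. The protocol thus holds three positions: restart allowed (Table 3 and the text around it), discontinuation possible (3.9) and restart barred (closing text of 6.7).

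**Step 5. Effect on the outputs.**

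- *Pooled AE summary (SAP Section 8.7.1).* Dose change, interruption and discontinuation form one category, overall and by SOC and PT. In course (a) the patient counts once in it, whether restarted or stopped.
- *Action taken (Protocol Section 6.3.3).* The recorded value would differ between a site that restarts and one that stops.
- *Exposure (SAP Section 8.5).* This is last dosing date minus first dosing date plus 1. The full treatment phase is 6 × 21 = 126 days. For a patient whose last dose before the event is on day d, exposure is d days if not restarted, and 126 days if restarted and continued to Cycle 6, Day 21. The difference is 126 − d. As an illustration, d = 42 (end of Cycle 2) gives 126 − 42 = 84 days.
- *Disposition (SAP Section 8.1).* The patient could appear as completing or as discontinued with a reason.

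**The case against.** The strongest reply is that the section can be read coherently. The *Other* row grants a permission, while the closing text bars restart and names the event. A specific exception limiting a general permission is an ordinary reading, and not restarting satisfies both passages. It would therefore go too far to infer that the protocol issues two opposite orders, because nothing in it requires a restart. That part stands. What remains is that the protocol never states this order of precedence, and a site using only the table would not see the exception.

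The safeguards also count. Suspected keratitis goes promptly to a specialist, the restart text provides for agreement with the study team physician as needed, and the local prescribing information may settle the matter. They lower the risk without removing the inconsistency: the consultation is conditional, the referral carries no dosing action, and the prescribing information is not among the documents reviewed.

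A last objection is that the synopsis lists keratitis, not corneal ulceration, for close monitoring. That is correct, so the point does not rest on that list.

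**Conclusion.** Section 6.7 is internally inconsistent on corneal ulceration, and Section 3.9 adds a third, softer wording. The direct conflict with Table 3 covers one of the three courses set out above: Grade 3 or higher, improving to Grade 0-2 within the hold.

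Three stronger readings are tempting but not supported.

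- *Section 3.9 independently mandates a permanent stop.* Its list says only that patients may be discontinued; the bar on restart comes from one sentence in 6.7.
- *Every grade is in conflict with the table.* The table agrees with the text when a Grade 3 or higher event does not improve, and says nothing below Grade 3.
- *The main AE results would be distorted.* The SAP pools interruption with discontinuation, so that summary hardly moves. The differences lie in action taken, exposure days and disposition.

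The documents give no rate for corneal ulceration, so no expected count can be stated. Each case would be one of the planned 60 patients (1/60 = 1.7%). The point matters because it concerns possible re-exposure of a patient in a safety trial, not because of its weight in the tables. It assumes that some sites would work from Table 3 without reading the section to its end.

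**What to change.** Reconcile Table 3, the text before it, the bullet after it, the closing text of Section 6.7 and Section 3.9 so that all give one action for corneal ulceration. Add an explicit entry or cross-reference in Table 3 and in the Keratitis paragraph, and state which passage prevails if they differ. Which action stands is for the sponsor's safety physician to decide; this review takes no position on it.

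The cost is one table entry, a few cross-references and a precedence sentence in a protocol amendment, with the approvals required by Section 10.5 and a notice to sites. No extra procedures, staff or patients are needed, and the SAP does not have to change.

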7.1 Concomitant and other treatments

As this study will be performed under clinical practice, the investigator may prescribe any other concomitant medication that he/she considers necessary for the patient as locally approved. Please refer to section 3.8 for restrictions.

7.2 Post Study Access to Study Treatment

The Treatment Phase will extend from Cycle 1, Day 1 to Cycle 6, Day 21; or until study drug discontinuation due to either disease progression or unacceptable toxicity; or other reasons whichever occurs first, as listed in Section 3.9. Patients may continue to receive osimertinib as long as they are continuing to show clinical benefit, as judged by the investigator, and in the absence of discontinuation criteria.

Patients receiving osimertinib at the time of study completion (i.e. after completion of treatment phase) may continue to receive osimertinib, if in the opinion of their treating physician they are continuing to derive clinical benefit from continued treatment or have not progressed clinically. They will be provided osimertinib treatment as per recommendation from treating physician on ethical basis. Post-trial access to osimertinib will be provided from local commercial supply though local distribution channel. Such patients will not be monitored after EOS visit.

8. Statistical Analyses by AstraZeneca

